11.1.2.2 Recording procedure

Any event meeting the definition of an AE / SAE must be collected and reported from subject signature of the informed consent and until 4 months after last GRASPA/ low-dose cytarabine administration (see Figure 4).

Any AE / SAE related to GRASPA according to investigator's opinion must be collected and reported throughout study duration.

Any SAE leading to death or life threatening must be collected and reported throughout study duration. **Figure 4: Safety reporting timeline guide**

All AE / SAE must be followed until resolution or the end of the protocol. The Investigator should ensure that adequate medical care is provided to the subject for any adverse event.

If there are several events and different symptoms combined to a main AE, then the only main AE (diagnostic preferable if available) should be recorded in the CRF. Where there is no link between different clinical symptoms occurring at the same time, each sign should be recorded as separate AE.

Occurrence and follow-up of AE should be assessed at each visit, and essential data listed hereafter should be recorded in the patient's CRF and patient's medical file as well:

- the severity or grade of the adverse event,
- the causality: determination of whether an adverse event is related to the investigational treatment or procedure, or other agents are suspected of causing the adverse event,
- the action(s) taken regarding investigational product (continued / interrupted / stopped)
- the corrective treatment if any
- the event outcome
- the seriousness of the event

11.1.2.3 Intensity /AE grading

Grade is used to denote the severity of the adverse event. The NCI Common Terminology Criteria for Adverse Event (NCI CTCAE) v. 4.0 will be used as reference for AE grading in this trial. If the term does NOT appear in the NCI CTCAE, the AE is graded using the following categories:

- 1 / Mild: minor; no specific medical intervention; asymptomatic laboratory findings only, radiographic only; marginal clinical relevance
- 2 / Moderate: minimal intervention; local intervention; noninvasive intervention (packing, cautery),
- **3** / **Severe**: significant symptoms requiring hospitalization or invasive intervention; transfusion; elective interventional radiological procedure; therapeutic endoscopy or operation). The term "severe" is often used to describe the intensity (severity) of a specific event. This is not the same as "serious," which is based on patient/event outcome or action criteria (see section 11.2).

- 4 / Life-threatening or disabling: complicated by acute, life-threatening metabolic or cardiovascular complications such as circulatory failure, hemorrhage sepsis. Life-threatening physiologic consequences; need for intensive care or emergent invasive procedure; emergent interventional radiological procedure, therapeutic endoscopy or surgery.
- 5 / Fatal

11.1.2.4 Causality assessment

Causality is the determination of whether an adverse event is related to a medical treatment or procedure. Causality categories are:

- **Reasonable possibility:** where the AE is clearly (certainly), likely to be (probably) or could be (possibly) related to the treatment or procedure.
- No reasonable possibility: where the AE is clearly NOT (not related) or doubtfully (unlikely) related to the treatment or procedure.
- In the case it is impossible to judge the AE causality, due to lack of information, or inconsistent information which cannot be investigated further, the AE/SAE will be reported as **possibly related**.

11.1.2.5 Outcome

The event outcome is mandatory and should be recorded as soon as it gets resolved, where appropriate when the subject has completed the protocol at the latest. The outcome should be one of the following:

- **Recovering**: the AE is improving
- Not yet recovered: the AE is still ongoing when the subject has completed the protocol.
- **Recovered**: fully recovered or by medical or surgical treatment the condition has returned to baseline level.
- **Recovered with sequelae**: as a result of the AE, the subject suffered persistent and significant disability/incapacity (e.g. became blind, deaf, paralyzed). Any AE recovered with sequelae should be declared as an SAE (see section 11.2).
- Fatal: any AE resulting in death should be declared as an SAE (see section 11.2).

11.2 Serious Adverse Events (SAE)

11.2.1 Seriousness criteria

An adverse event is classified as "serious" when at least one the following criterion is met:

- **Results in death**: be aware that a death cannot be an event but always the outcome of an event. Exception is when death occurs suddenly, without the exact cause is stated. In this case only, the event should be recorded as "sudden death" with the seriousness criterion "fatal" indicated.
- Is life-threatening: life-threatening in the definition of a serious adverse event refers to an event in which the subject was at risk of death at the time of event; it does not refer to an event which hypothetically might have caused death if it was more severe.
- Requires inpatient hospitalization or prolongation of existing hospitalization.
- Results in persistent or significant disability/incapacity.
- Is a congenital anomaly or birth defect.
- Is considered as serious according investigator judgment in other situation. Important adverse events/ reactions that are not immediately life-threatening or do not result in death or hospitalization but may jeopardize the subject or may require intervention to prevent one of the other outcomes listed above, should also be considered serious.

11.2.2 SAE procedures (notification)

In addition to be recorded in patient's CRF, as well as any Adverse Event, Serious Adverse Event will be recorded in a separate SAE form (Appendix 10), and declared to ERYTECH Pharma, whether attributed to the protocol or not.

Therefore, an SAE report must be completed and faxed without delay and in any case within 24 hours of obtaining knowledge about the event to:

SAE [contact] or email to [contact]

(Vigipharm mandated by ERYTECH Pharma)

If necessary, Investigator will be asked for additional information. SAE Follow-up report will be then completed and faxed to ERYTECH Pharma in the same way as the initial report.

Any documentation regarding SAE, initial and follow-up report, should be archived together with patient's source documents.

ERYTECH Pharma is responsible for declaring all Unexpected Serious Adverse Reactions (treatment related events) to Competent Authorities (and Ethical Committee(s) as needed), in accordance with the local requirements. Investigators will be informed as well.

11.2.3 SAE follow-up

Investigator should ensure that adequate medical care is provided to the subject for any adverse event.

All SAE must be followed until the subject has recovered, stabilized, recovered with sequelae or died. The Investigator must forward follow-up information on SAE to ERYTECH Pharma without delay and in any case within 24 hours of obtaining the new information. SAE Follow-up report should be faxed accordingly to:

SAE [contact] or email to [contact]

(Vigipharm mandated by ERYTECH Pharma)

11.3 Event linked to red blood cells during GRASPA administration

Any adverse event that may be related to erythrocytes / blood transfusion should be assessed by the investigator according to the clinical background of the patient. In such cases, the Appendix 8 summarizes the corresponding procedure:

- Any event linked to red blood cells will be recorded in the CRF as an AE. If seriousness criterion is met, a SAE should be declared to ERYTECH Pharma drug safety, completing SAE report form (see section 11.2.2 above).
- The return of the bag of GRASPA to ERYTECH Pharma will be organized for immunologic and hematologic analyses.
- If additional analyses are required in local laboratory, segment tubes can be removed from the bag of GRASPA for this purpose.

11.4 Pregnancy - Lactation

Since no preclinical or clinical data are available, GRASPA IS NOT TO BE USED during pregnancy and lactation.

Cytarabine has known teratogen effects in several animal species and IS NOT TO BE USED during pregnancy and lactation

11.5 Trial premature withdrawal

The trial can be prematurely stopped (definitely or temporarily) when:

• The treatment is considered as too noxious to continue with further clinical investigations

- Occurrence of new fact that can modify ERYTECH Pharma / Competent Authority approval on the trial, or for any unethical reason
- ERYTECH Pharma decision to stop product development

In case of any reason motivating such withdrawal, the Investigator should promptly inform the patients, ensure appropriate therapy and follow-up, and complete the CRF with all available data at the time of trial arrest.

Trial withdrawal with the reason will be declared to Competent Authority (and EC if applicable) in accordance with local requirements.

11.6 Independent Data Monitoring Committee

An Independent Data Monitoring Committee (IDMC) will review the safety and tolerability of GRASPA at the following time points:

- when 30 patients have been enrolled, to evaluate limiting toxicities as defined in stopping rules,
- when 60 patients have been enrolled.

The original remit of the IDMC was to review the efficacy of GRASPA following 60 PFS events. The IDMC meeting will still take place following the accrual of these events, but with remit of safety review only. Thereafter, the IDMC will convene every 6 months for safety review

Specific attention will be paid on patients with type II diabetes treated with oral hypoglycemic agents: IDMC will assess 5 first of those patients enrolled after at least one month follow-up, and may reconsider study enrollment of such patients.

To avoid any conflict between the evaluation of safety and the primary efficacy endpoint OS, deaths in the study will be presented to the IDMC only in terms of overall frequencies and individual patient narratives. In particular Kaplan-Meier curves and p-value comparisons of those curves will not be presented.

The IDMC will work completely independently of the sponsor. Sponsor representatives will not attend those meetings of the IDMC where study data aggregated by treatment group will be considered. A specific document will be edited separately providing IDMC members details and conditions for such evaluation during IDMC meetings.

11.7 Development Update Safety Report (DSUR)

ERYTECH Pharma will forward to Competent Authority and Ethic Committee Development Update Safety Report on GRASPA with all available safety information, in accordance with local requirements.

ERYTECH Pharma will keep investigators informed about data available impacting subject's safety.

Occurrence of any new fact about research conduct or investigational product use, likely to cause subject's safety impairment will be taken into account to initiate appropriate action to guarantee subject's safety. ERYTECH Pharma will immediately inform Competent Authority and Ethic Committee as well as investigators.

12. Case Record Form (CRF)

CRF will be used to collect data. Any assessment and corresponding results performed during protocol visits as stated in the schedule (detailed in section 8) will be recorded in patient medical file (source document) in order to be integrated in the Case Record Form.

All laboratory data and Investigator observations must be reported to sponsor. Any imaging techniques must be summarized in the CRF where applicable. The original reports, traces and films must be retained by the Investigators for future reference.

Some data may not be included in source document but could be recorded in the CRF directly. Such data need to be defined before study start. The CRF will be then considered as a part of source document.

This trial will use an e-CRF, i.e. based on electronic data capture (EDC), designed and provided by ERYTECH Pharma or contractors. All requested data should be entered in the CRF on a regular basis, as soon as they are obtained, by the investigator or an authorized delegated person. The Investigator or authorized staff must ensure that all information recorded is consistent with the source information.

At the end of the study, each CRF will be edited for archiving purposes, in accordance with local requirements.

13. Monitoring procedures

During the course of the trial, a dedicated CRA will visit investigational sites to monitor study conduct as it progresses. The purpose of these visits is to ensure:

- Subjects enrolled were duly informed and gave their consent,
- Adherence to protocol and GCP guidelines are followed,
- CRF completion is accurate (consistency of data recorded versus source document),
- SAE are notified accordingly if any,
- Drug accountability is well documented, and documentation regarding investigational product is present and complete,
- Any problems detected in the course of the monitoring visits are resolved.

Therefore, the Monitor must be given direct access to source documents (original documents, data and records, see section 16). Direct access includes permission to examine, analyze, verify and reproduce any record(s) and report(s) that are important for clinical trial evaluation.

Investigator must be available for discussions and clarifications over the phone as well.

The following data can be recorded directly on the CRF and will be considered as source data: Vital signs. For all other data in the CRF, it must be possible to verify these against source documents.

Computerized data controls will be performed as well and may raise queries where there are inconsistencies. Investigator will be then requested to answer queries as soon as possible.

14. Data Management

The subjects will be identified by subject number, initials, site, and trial identification number. Appropriate measures such as encryption or deletion will be enforced to protect the identity of human subjects in all presentations and publications as required by local/regional/national requirements.

Electronic data transfer of any CRF or subject related data must be approved by the responsible Data Management Unit(s). In cases where data is transferred via non-secure electronic networks, data must be primarily encrypted.

15. Statistics

15.1 Analysis sets (rules for statistical population definition)

The intent-to-treat (ITT) efficacy population will be comprised of all randomized patients in the groups to which they were randomly assigned, regardless of their adherence with the entry criteria, regardless of the treatment they actually received, and regardless of subsequent withdrawal from treatment or deviation from protocol.

The per-protocol (PP) efficacy population will be comprised of all patients from the ITT population without major protocol deviation that have received trial product and have completed at least one course of treatment.

The safety population will be comprised of all patients that have received at least one administration of trial products.

Patients without progression or death will be included in the efficacy population with a time interval that is right censored.

The responsibility for excluding patients from the analysis will be a joint decision by Sponsor, Statistician, Investigator and Trial Monitor. The patients to be excluded and the reasons for their exclusion must be documented and signed by those responsible prior to database release. The documentation must be stored together with the remaining trial documentation.

15.2 Sample size calculation

The sample size calculation is based on the original primary efficacy endpoint (PFS). We assumed 75% improvement in median PFS in the L-asparaginase (GRASPA) plus low-dose cytarabine group compare to median PFS in the low-dose cytarabine group (control). An hypothesis of 24 months of accrual time and whole study duration of 48 months is used. No dropout rate was taken into consideration.

With a two-sided 5% level significance test and a power of 80%, taking into account the unbalanced group size (2 : 1), a total of 117 patients should be enrolled to observe 117 events (78 in the L-asparaginase (GRASPA) plus low-dose cytarabine and 39 in the low-dose cytarabine group).

The study size had been increased to 123 patients (41 patients in Arm A and 82 patients in Arm B) in order to incorporate an interim analysis for futility. This interim analysis however will not now be undertaken.

15.3 Statistical methods

A statistical analysis plan (SAP) will be prepared by the CRO and validated by the sponsor. Statistical analyses will be performed with SAS[®] version 9.2 or higher (SAS institute, North Carolina, USA).

A primary report will be delivered after 12-months follow-up of last patient included. An addendum on 24-months follow-up period will be added for the final report.

Any patient not known to have had an event (death/progression) at the time of analysis will be censored based on the last recorded date on which the patient was known to be event-free.

For numeric secondary endpoints (e.g. quality of life scores) and depending on the number of missing/invalid data, a data replacement according to the Last Observation Carried Forward method will be performed as a sensitivity analysis.

Missing days and/or months for dates pertaining to events far before the initiation of the study will be replaced by 15 and/or June respectively for time calculations purposes.

Other conventions may be specified in the study statistical analysis plan.

15.3.1 Primary endpoint analysis

The primary endpoint will be analyzed based on the ITT population. Efficacy data will also be analyzed on the Per-Protocol population to assess sensitivity of results to protocol compliance.

The primary objective of the trial is to estimate whether GRASPA plus low-dose cytarabine is more promising than low-dose cytarabine alone with respect to OS in subjects 65-85 years old with newly diagnosed AML unfit for intensive chemotherapy. OS will be calculated from date of randomization to date of death (or censoring).

OS will be summarized using Kaplan-Meier methods. The analysis of OS, will be performed using a stratified log-rank test (stratification factor PS (0, 1 vs 2) to compare treatment groups).

Hypothesis testing will be based on the following relations:

H0 : $\theta = -\log(\lambda) = 0$ and the alternative hypothesis will be H1 : $\theta = \theta 1 > 0$ where λ is the hazard ratio (HR) between the GRASPA plus low-dose cytarabine and the low-dose cytarabine alone groups. In our case (assumption for the median survival times of 2 months and 3.5 months for low-dose cytarabine alone and GRASPA plus low-dose cytarabine respectively) this will mean that H1 : $\theta = -\log(0.5714) = 0.5597$.

A secondary analysis will be performed using Cox's proportional hazards regression model, allowing for the effect of treatment and prognostic factors (ECOG, age and cytogenetic group). For the main criterion of efficacy the significance level will be 0.05 using a two-sided test.

The primary analysis for OS will take place once all patients have completed 12 months in the study. It should be noted however that the study is not powered explicitly for OS and statistical significance in favor of GRASPA plus low-dose cytarabine is not anticipated. A decision as to whether GRASPA appears to be a promising drug in this indication will be based on the numerical values for the hazard ratio for OS. A hazard ratio of ≤ 0.80 will indicate a 20% numerical reduction in the death rate on average over time in the GRASPA group compared to control.

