Treatment discontinuation	 Patients will discontinue study treatment in the following situations: Disease relapse or presence of a resistant disease, unless the investigator considers that the patient has a clinical benefit from continuing the treatment. In this case, the investigator should continue to perform the same 								

– CONFIDENTIAL –										
	study visits as long as considered clinical beneficial.									
	Occurrence of GRASPA-related toxicity, such as:									
	• Grade 3 or 4 pancreatic toxicity									
	 Grade 3 or 4 hepatic toxicity, allergic reaction, or coagulation event 									
	 other non-hematologic Grade 4 toxicity 									
	Patient assessment should continue as planned until evidence of relapse or presence of a resistant disease, in which case, patient will be followed up for survival.									
	Patient unwilling to continue									
	No evidence of study treatment benefit at investigator's decision									
Statistical plan	Sample Size									
	The sample size calculation has been based on the original primary efficacy endpoint (PFS) and a study that included an interim analysis for futility. We assumed 75% improvement in median PFS in the GRASPA plus low-dose cytarabine group compared to median PFS in the low-dose cytarabine group (control). With a two-sided 5% level significance test and a power of 80%, taking into account the unbalanced group size (2 : 1) and interim analysis a total of 123 patients should be enrolled (82 in the GRASPA plus low-dose cytarabine and 41 in the low-dose cytarabine group).									
	Analysis plan									
	The primary objective of the trial is to estimate whether GRASPA plus low-dose cytarabine is more promising than low-dose cytarabine alone with respect to OS in subjects 65-85 years old, with newly diagnosed AML unfit for intensive chemotherapy. The study however is not powered explicitly for OS and statistical significance in favor of GRASPA plus low-dose cytarabine is not anticipated. A decision as to whether GRASPA appears to be a promising drug in this indication will be based on the numerical values for the hazard ratio for OS. A hazard ratio of ≤ 0.80 will indicate a 20% numerical reduction in the death rate on average over time in the GRASPA group compared to control.									

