This is a phase 2 proof of concept study and all efficacy parameters will be considered as the basis for conclusions regarding the activity of GRASPA in this population. P-values will be calculated for analyses of the primary endpoints in all patients. A two-sided 0.05 level of significance will be used as a guidance for interpretation of the data, but strict statistical significance will not be the only basis on which efficacy will be judged. In particular, the conclusions will not be based solely on the primary analysis of the primary endpoint. As indicated at the advisory board meeting, a Hazard Ratio (HR) less than 0.8 would indicate an interesting level of activity (approximately an increase in median OS from 6.4months to 8.0 months), which would warrant further investigation in a Phase 3. The activity of GRASPA will be concluded collectively in relation to the clinical relevance as indicated by the magnitude of effect across a range of endpoints (the totality of evidence).

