5. STATISTICAL METHODS

5.1. Sample Size Justification

The sample size calculation is based on the original primary efficacy endpoint (PFS). We assumed 75% improvement in median PFS in the GRASPA plus LDAC group (treatment) compared to median PFS in the LDAC group (control). This corresponded to a median PFS of 2 months for the null hypothesis and a median of 3.5 months for the alternative hypothesis. An assumption of 24 months of accrual time and whole study duration of 48 months was used. No dropout rate was taken into consideration.

With a two-sided 5% level significance test and a power of 80%, taking into account the unbalanced group size (1 : 2), a total of 117 patients should be enrolled in order to observe 117 PFS events.

The study was designed based on the initial primary endpoint using group sequential methodology, allowing for interim analysis for futility. In order to account for this, the sample size was increased from 117 to 123 patients (41 in the LDAC group and 82 in the GRASPA plus LDAC group).

However, the sponsor amended the study, and the primary endpoint was changed from PFS to OS. It is acknowledged that the study is not powered to detect a statistically significant difference in OS; rather this is a proof of concept signal seeking study. In light of this, the one-sided significance level will be 0.025.

A decision as to whether GRASPA appears to be a promising drug in this indication will be based on the numerical values for the hazard ratio for OS. A hazard ratio of ≤ 0.80 will indicate a 20% numerical reduction in the death rate on average over time in the GRASPA group compared to control.

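### Does stating the OS alternative with the original PFS planning medians (2 vs 3.5 months) require a change to the plan?

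*Protocol*

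**What the plan says.** Protocol 15.3.1 covers the primary endpoint, OS, measured from randomization to death. After specifying a log-rank test stratified by performance status, it says "Hypothesis testing will be based on the following relations". The null is θ = −log(λ) = 0 and the alternative is a positive value θ1, where λ is the hazard ratio of GRASPA plus low-dose cytarabine to low-dose cytarabine alone. The value of θ1 rests on an "assumption for the median survival times of 2 months and 3.5 months for low-dose cytarabine alone and GRASPA plus low-dose cytarabine respectively", which gives HR 0.5714 and θ1 = 0.5597.

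The same section adds "For the main criterion of efficacy the significance level will be 0.05 using a two-sided test". It warns that "the study is not powered explicitly for OS and statistical significance in favor of GRASPA plus low-dose cytarabine is not anticipated", and it bases the judgement of promise on the observed OS hazard ratio, with 0.80 as the mark.

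Elsewhere the effect is attached to PFS:
- Protocol 15.2: "We assumed 75% improvement in median PFS in the L-asparaginase (GRASPA) plus low-dose cytarabine group compare to median PFS". The synopsis says the same. Neither gives the two medians.
- SAP 5.1: "This corresponded to a median PFS of 2 months for the null hypothesis and a median of 3.5 months for the alternative hypothesis".

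For OS, SAP section 1 illustrates a hazard ratio of 0.8 as "approximately an increase in median OS from 6.4months to 8.0 months".

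**The concern.** The formal alternative for the primary endpoint carries an effect that was set for a different endpoint. Section 15.3.1 does not mention PFS, and 15.3.1 is the only place where the protocol gives 2 and 3.5 months as planning medians. A reader with the protocol alone could conclude that the sponsor expected a median OS of 2 months on control and an OS hazard ratio of 0.57.

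That reading fits badly with the rest of the section. An OS effect of that size would be detectable with 123 patients, yet the section says OS is not explicitly powered and that significance is not expected. If the figure were a working OS assumption, the protocol and SAP would disagree about the design effect. A study report could then cite 0.5714 as a pre-specified OS target that nobody had set.

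**Working it through.** **Inputs.** Medians 2 and 3.5 months, HR 0.5714 and θ1 0.5597 (protocol 15.3.1; the medians also in SAP 5.1, as PFS). A 75% gain in median PFS, two-sided 5%, 80% power, 2:1 allocation, 117 events from 117 patients (78 and 39), raised to 123 (82 and 41) for a futility look that was later dropped (protocol 15.2). OS mark HR ≤ 0.80 (protocol 15.3.1).

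**Step 1: the stated effect.** With exponential times, HR = 2/3.5 = 0.5714. −ln(0.5714) = 0.5597 from the rounded ratio, or 0.5596 unrounded. The 75% gain is 3.5/2 = 1.75, and ln(1.75) = 0.5596. The arithmetic in 15.3.1 is right, and the effect equals the PFS planning effect.

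**Step 2: the plan's sizing.** Schoenfeld's formula, allocation 1/3 to 2/3:

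- Events for 80% power = (1.960 + 0.8416)² / [(2/9) × 0.5596²] = 112.8, so 113.
- Power at 117 events = Φ(0.5596 × √(117 × 2/9) − 1.960) = Φ(2.853 − 1.960) = 81.4%.
- A simulated log-rank test with 39 and 78 patients, all with events (6,000 runs), gave 80.1%.

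The event count is 4 below the stated 117, so this formula does not reproduce it exactly. The power does agree with the stated 80%. The effect printed under OS is the one behind the PFS sample size.

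**Step 3: where θ1 could act in the OS analysis.**

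| Element | Source | Uses θ1? |
|---|---|---|
| Stratified log-rank test | Protocol 15.3.1, SAP 5.6 | No: observed minus expected deaths under θ = 0 |
| Significance level | Protocol 15.3.1, SAP 5.1 and 5.2.1 | No |
| Hazard ratio and 95% CI | SAP 5.6, stratified Cox model | No: estimated from the data |
| Timing of the primary analysis | Protocol 15.3.1: 12 months completed by all patients | No: set by calendar, not by events |
| Sample size | Protocol 15.2, SAP 5.1 | Only as the PFS effect, and labelled PFS there |
| Judgement of promise | Observed OS HR ≤ 0.80 | No |
| Interim look | None | No |

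A numerical alternative matters for power, for an event target or for conditional power at an interim look. None of these is defined for OS here.

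**Step 4: what the figure would imply if read as OS.** Take the upper limit, all 123 patients dead:

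- HR 0.5714: Φ(0.5596 × √(123 × 2/9) − 1.960) = Φ(2.926 − 1.960) = 83.3%.
- HR 0.80 (θ = 0.2231): Φ(0.2231 × √(123 × 2/9) − 1.960) = Φ(1.167 − 1.960) = 21.4%.

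Power of about 83% does not sit with the statement that OS is not explicitly powered. That supports reading the sentence as a carry-over. It does not reveal a second, competing OS design.

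**The case for a change.** The strongest case for a correction is that this is the formal hypothesis for the primary endpoint. The section defines OS just before it, the protocol never labels these medians as PFS, and the remedy would be one sentence. All of that is true. The words used for the medians could loosely cover PFS, but in that section the natural reading is OS, so the label is wrong.

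What does not stand is the claim of consequence. A protocol reader finds in 15.2, immediately before, that the sizing rests on PFS with a gain of exactly this ratio, and finds in 15.3.1 itself that OS was not the basis of the power. The analyst works from the SAP, which identifies the medians as PFS and specifies the OS analysis without θ1. The OS illustration of 6.4 to 8.0 months cannot show what the protocol intended, because the SAP attributes it to an advisory board of January 2017, after protocol version 7 of October 2015.

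It might also be said that a positive θ1 conflicts with a two-sided test. It does not: a design alternative in the direction of benefit beside a two-sided test is ordinary practice. Whether the primary test is two-sided at 0.05 (protocol 15.3.1, SAP section 1) or one-sided at 0.025 (SAP 5.1 and 5.2.1) is a separate question. Rewriting the hypothesis here would not settle it.

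**Conclusion.** The mislabel is real: protocol 15.3.1 presents the PFS planning effect (2 vs 3.5 months, HR 0.5714, θ1 0.5597) as the OS alternative. It is a clerical carry-over from the change of primary endpoint that version 7 records in Appendix 11. Correcting it would change no test, significance level, sample size, analysis date, decision rule or result, so no change to the plan is called for. The size of the effect is zero on every OS output. The remaining risk is a misquoted design effect in a report, and SAP 5.1 already guards against that.

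This rests on two things that the documents support: the OS analysis follows SAP 5.6, and no OS power, event target or interim look depends on θ1. The power figures assume proportional hazards, and the conversion of medians to a hazard ratio assumes exponential times. The conclusion needs neither assumption.
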